11.5.2. Titration Phase: Visit 2 (Week 1, Day 1)

- Review of inclusion/exclusion criteria.
- Record concomitant medications.
- Obtain vital signs and body weight.
- For females of childbearing potential, obtain sample for urine pregnancy test (to be confirmed with serum pregnancy test if positive).
- Record LAEP.
- Record AEs.
- Dispense study drug.
- Collect paper seizure diary.
- Distribute paper seizure diary.
- Review seizure diaries.
- Administer questionnaires (EQ-5D, QOLIE-31, POMS-SF, NDDI-E, MOAS, and eC-SSRS).

11.5.3. Start of Maintenance: Visit 3 (Week 3 \pm 3 days)

- Record concomitant medications.
- Perform physical and neurological examination.
- Obtain vital signs and body weight.
- For females of childbearing potential, obtain sample for urine pregnancy test (to be confirmed with serum pregnancy test if positive).
- Record LAEP.
- Record AEs.
- Dispense study drug.

- Collect study drug.
- Record any ESL dose change since the last study visit.
- Record any AED dose change since the last study visit.
- Collect paper seizure diary.
- Distribute paper seizure diary.
- Review seizure diaries.
- Administer the questionnaires (CGI-I, PGI-C, and eC-SSRS).

11.5.4. Visit 4 (Week 7 ± 3 days)

- Record concomitant medications.
- Perform physical and neurological examination.
- Obtain vital signs and body weight.
- Collect a saliva sample for characterization of HLA and Questionnaire (optional, for subjects who have signed optional genetic consent and who have been tolerant of ESL without rash or allergic reaction for at least 6 weeks).
- For females of childbearing potential, obtain sample for urine pregnancy test (to be confirmed with serum pregnancy test if positive).
- Record LAEP.
- Record AEs.
- Dispense study drug.
- Collect study drug.
- Record any ESL dose change since the last study visit.
- Record any AED dose change since the last study visit.
- Collect paper seizure diary.
- Distribute paper seizure diary.
- Review seizure diaries.
- Administer the eC-SSRS questionnaire.

11.5.5. Telephone Call 1 (Week 9 ± 3 days)

- Record AEs.
- Record any ESL dose change since the last study visit.
- Record any AED dose change since the last study visit.

11.5.6. Visit 5 (Week 11 ± 3 days)

- Record concomitant medications.
- Perform physical and neurological examination.
- Obtain vital signs and body weight.
- For females of childbearing potential, obtain sample for urine pregnancy test (to be confirmed with serum pregnancy test if positive).
- Record LAEP.
- Record AEs.
- Dispense study drug.
- Collect study drug.
- Record any ESL dose change since the last study visit.
- Record any AED dose change since the last study visit.
- Collect paper seizure diary.
- Distribute paper seizure diary.
- Review seizure diaries.
- Administer questionnaires (EQ-5D, CGI-I, PGI-C, QOLIE-31, POMS-SF, NDDI-E, MOAS, and eC-SSRS).

11.5.7. Visit 6 (Week 15 ± 3 days)

- Record concomitant medications.
- Perform physical and neurological examination.
- Obtain vital signs and body weight.
- For females of childbearing potential, obtain sample for urine pregnancy test (to be confirmed with serum pregnancy test if positive).
- Record LAEP.
- Record AEs.
- Dispense study drug.
- Collect study drug.
- Record any ESL dose change since the last study visit.
- Record any AED dose change since the last study visit.
- Collect paper seizure diary.
- Distribute paper seizure diary.
- Review seizure diaries.

- Administer the eC-SSRS questionnaire.

11.5.8. Telephone Call 2 (Week 17 ± 3 days)

- Record AEs.
- Record any ESL dose change since the last study visit.
- Record any AED dose change since the last study visit.

11.5.9. Visit 7 and Visit 8 (Week 19 ± 3 days and Week 23 ± 3 days)

- Record concomitant medications.
- Perform physical and neurological examination (Visit 8 only).
- Obtain vital signs and body weight.
- For females of childbearing potential, obtain sample for urine pregnancy test (to be confirmed with serum pregnancy test if positive).
- Record LAEP.
- Record AEs.
- Dispense study drug.
- Collect study drug.
- Record any ESL dose change since the last study visit.
- Record any AED dose change since the last study visit.
- Collect paper seizure diary
- Distribute paper seizure diary
- Review seizure diaries.
- Administer the eC-SSRS questionnaire.

11.5.10. End of Maintenance/End of Study: Visit 9 (Week 27 ± 3 days)

- Record concomitant medications.
- Perform physical and neurological examination.
- Obtain vital signs and body weight.
- Perform a 12-lead ECG.
- For females of childbearing potential, obtain blood for serum β -hCG.
- Obtain blood sample and urine sample for clinical laboratory testing (including thyroid panel).
- Record LAEP.
- Record AEs.

- Dispense study drug if needed for taper (Note: Subjects who elect to continue on commercially available drug will not be dispensed additional ESL at this visit. Subjects who elect to discontinue ESL will be provided sufficient ESL to accommodate the appropriate taper regimen.)
- Collect study drug.
- Record any ESL dose change since the last study visit.
- Record any AED dose change since the last study visit.
- Collect paper seizure diary
- Distribute paper seizure diary
- Review seizure diaries.
- Administer questionnaires (EQ-5D, CGI-I, PGI-C, QOLIE-31, POMS-SF, NDDI-E, MOAS, and eC-SSRS).
- Ensure return of watch and data collection device.

11.5.11. Early Discontinuation Visit

Subjects who withdraw prior to the EOS visit should have an early discontinuation visit (EDV) within 72 hours. Every effort should be made for all subjects prematurely discontinuing the study drug, regardless of cause, to undergo final evaluation described below:

- Record concomitant medications.
- Perform physical and neurological examination.
- Obtain vital signs and body weight.
- Perform a 12-lead ECG.
- For females of childbearing potential, obtain blood for serum β -hCG.
- Obtain blood and urine sample for clinical laboratory testing (including thyroid panel).
- Record LAEP.
- Record AEs.
- Collect study drug.
- Record any AED dose change since the last study visit.
- Collect paper seizure diary
- Distribute paper seizure diary
- Review seizure diaries.
- Administer questionnaires (EQ-5D, CGI-I, PGI-C, QOLIE-31, POMS-SF, NDDI-E, MOAS, and eC-SSRS).
- Dispense study drug if needed for taper.
- Ensure return of watch and data collection device.

11.5.12. Follow-up Visit: Visit 10 or Telephone Call 3 (Week 31 ± 7 days)

- Record AEs.
- Record concomitant medications.
- Review paper seizure diary.

12. SAFETY REPORTING

12.1. Definitions

12.1.1. Adverse Events

An AE is any untoward medical occurrence temporally associated with the use of a drug in humans, whether or not considered drug related.

Untoward medical occurrences that occur between the time of signing the ICF and first drug administration are pre-treatment events. Those that occur after first administration of study drug are considered AEs.

An AE can, therefore, be any unfavorable and unintended sign (including an abnormal laboratory finding), symptom, or disease occurring after the administration of a medicinal (investigational) product, whether or not considered related to the medicinal (investigational) product. AEs may include the onset of new illness and the exacerbation of pre-existing conditions.

In this study, seizures should not routinely be considered as AEs. Individual seizures (including clusters of seizures and status epilepticus) which are sufficiently severe to require intervention beyond what is usual for the subject or hospitalization may be recorded as AEs. Worsening of seizures (either in severity, pattern, type, or frequency) and injury or other adverse consequences of seizures should be recorded as AEs.

The Investigator should attempt to establish a diagnosis of the event based on signs, symptoms, and/or other clinical information. In such cases, the diagnosis should be documented as the AE and not the individual signs/symptoms.

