12.1.2. Serious Adverse Events

A SAE is an AE that meets one or more of the following criteria:

- Results in death.
- Is life-threatening.
- Requires hospitalization or prolongation of existing hospitalization.
- Results in persistent or significant disability or incapacity.
- Is a congenital anomaly or birth defect.
- Is an important medical event that may jeopardize the subject or may require a medical or surgical intervention to prevent one of the outcomes listed above.

Examples of such medical events include allergic bronchospasm requiring intensive treatment in an emergency room or at home, or blood dyscrasias.

The term “severe” is often used to describe the severity of a specific event (as in mild, moderate, or severe myocardial infarction) (see [Section 12.3](#)); the event itself, however, may be of relatively minor medical significance (such as severe headache). This is not the same as “serious,” which is based on subject/event outcome or action criteria usually associated with events that pose a threat to a subject’s life or functioning as defined by the criteria above.

During the study, if a subject has a hospitalization or procedure (eg, elective surgery) that was scheduled before the study entry, ie, before informed consent for an event/condition that occurred before the study, the hospitalization is considered a therapeutic intervention and not the result of a SAE. However, if the event/condition worsens during the study, it should be reported as an AE (or SAE, if the event/condition results in a serious outcome such as prolongation of hospitalization).

Life-threatening means that the subject was, in the view of the Investigator, at immediate risk of death from the event as it occurred. This definition does not include an event that had it occurred in a more severe form might have caused death.

SAE criteria information will be captured on the CRF.

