12.3. Collection and Recording of Adverse Events

All pre-treatment events and AEs must be recorded in the subject's study records/source documents. All pre-treatment events must be recorded on the CRF. All AEs must be recorded on the CRF from first dose administration through the final study visit. All SAEs must be recorded on the CRF from the time informed consent/assent is obtained through the final study visit.

All AEs will be followed until resolution, stabilization of the condition, the event is otherwise explained, or the subject is lost to follow-up.

Each AE is to be evaluated for duration, severity, frequency, seriousness, action taken with the study treatment, outcome, and causal relationship to the study treatment. Definitions for severity, frequency, action taken with the study treatment, outcome, and causal relationship to the study treatment are presented below.

The severity of AE:

- **Mild** – Ordinarily transient symptoms that do not influence performance of subject's daily activities. Other treatment is not ordinarily indicated.
- **Moderate** – Marked symptoms sufficient to make the subject uncomfortable. Moderate influence on performance of subject's daily activities. Other treatment may be necessary.
- **Severe** – Symptoms cause considerable discomfort. Substantial influence on subject's daily activities. May be unable to continue the study, and other treatment may be necessary.

The frequency of AE:

- **Once** – an isolated episode.
- **Intermittent** – occurs on 2 or more separate occasions.
- **Continuous** – does not abate from date of onset to date of resolution.

The action taken with the study treatment:

- **Drug Interrupted** – Study drug stopped temporarily.
- **Drug Withdrawn** – Study drug stopped permanently.
- **Dose Reduced**.
- **Dose Increased**.
- **Dose Not Changed**.
- **Not Applicable**.
- **Unknown**.

The outcome of the AE:

- **Recovered/Resolved**.
- **Recovering/Resolving**.

- **Not Recovered/Not Resolved.**
- **Recovered/Resolved with Sequelae.**
- **Fatal.**
- **Unknown.**

The causal relationship of the AE to the study treatment:

- **Not related**
 - **Not related** – Improbable temporal relationship and is plausibly related to other drugs or underlying disease.
- **Related**
 - **Possible** – occurred in a reasonable time after study drug administration, but could be related to concurrent drugs or underlying disease.

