12.4.1. Serious Adverse Event

If the Investigator or study center staff becomes aware of a SAE that occurs in a study subject after obtaining informed consent through 30 days following the last dose of the study medication, this must be reported immediately to the Sponsor whether considered related or unrelated to the study drug. SAEs must be recorded on the CRF and the data recorded should agree with that on the SAE form.

SAEs will be followed until resolution, loss to follow-up, stabilization of condition, or the event is otherwise explained.

In addition to the initial telephone notification, an initial SAE form as applicable must be completed and signed and sent via fax or email (see Table 1) to PPD Pharmacovigilance

(PPD-PVG) within 1 business day of the Investigator or study center staff becoming aware of the event. The SAE form must be signed by the Investigator or appropriate designee. PPD-PVG provides the SAE form used to report SAEs.

The Sponsor or designee will promptly notify all study centers and Investigators of a SAE that is determined to be expedited to the Regulatory Authorities in accordance with applicable law(s) and regulation(s). These SAEs must be promptly reported to the Institutional Review Board (IRB) or Independent Ethics Committee (IEC) by the Principal Investigator or the appropriate person at the study center if required per IRB/IEC guidelines.

If an SAE is reported after participation of the study, the Investigator or an authorized delegate should report SAEs “spontaneously” to PPD-PVG if considered at least possibly related to the study drug.

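### A seizure admission that the site does not judge to be a worsening or an adverse consequence may be left unrecorded as an AE, and then cannot be counted as an SAE

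*Protocol*

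**What the plan says.** Protocol Section 12.1.1 starts from an exemption: "In this study, seizures should not routinely be considered as AEs". It then deals with individual seizures, expressly including clusters and status epilepticus, that are "sufficiently severe to require intervention beyond what is usual for the subject or hospitalization may be recorded as AEs". The sentence after that is firmer: "Worsening of seizures (either in severity, pattern, type, or frequency) and injury or other adverse consequences of seizures should be recorded as AEs".

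Section 12.1.2 builds seriousness on top of AE status: "A SAE is an AE that meets one or more of the following criteria". One of the criteria is "Requires hospitalization or prolongation of existing hospitalization".

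Once an event is an SAE, the duties are strict. Section 12.3 says "All SAEs must be recorded on the CRF from the time informed consent/assent is obtained through the final study visit". Section 12.4.1 says of an SAE that "this must be reported immediately to the Sponsor whether considered related or unrelated to the study drug".

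The number and percentage of subjects with SAEs is a safety endpoint (Protocol Section 6.4, SAP Section 2.4.4). SAP Section 16.1.5 counts as SAEs only the events marked as serious on the adverse event source.

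**The concern.** The permissive verb falls on events that meet a seriousness criterion by their own description. If a site does not enter such an admission as an AE, the definition in 12.1.2 is never reached, and neither is the duty to report to the sponsor. Two sites could treat the same kind of admission differently, and each could point to the text.

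Two things are at stake. One is the SAE count, which can only lose events in this way and may vary by site for reasons unrelated to the drug. The other is central oversight. The study is open-label and has no data monitoring committee (SAP Section 4.1), so immediate SAE reports are a main route by which the sponsor learns of a serious event.

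**Working it through.** The plan gives no figure on this point, so the main check is to follow one event through the rules.

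**Step 1. Is the event an AE?** Take a subject admitted to hospital for a seizure.
- The exemption in 12.1.1 takes ordinary seizures out.
- The following sentence brings back seizures that need hospitalization or unusual intervention, but with *may*.
- The sentence after that uses *should*, for worsening in severity, pattern, type or frequency and for injury or other adverse consequences. Admission is not on that list.
- Section 12.2, by contrast, says that clinically significant laboratory, ECG and examination findings *will* be recorded as AEs.

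The answer therefore turns on a site judgement. If the episode is a worsening or has an adverse consequence, it should be recorded. If it is neither, recording is optional even though the subject was admitted.

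**Step 2. Is the event an SAE?** Section 12.1.2 tests only events that are already AEs. An admission not recorded at Step 1 is never tested against the hospitalization criterion.

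**Step 3. Do the compulsory rules catch it?** The SAE rules in 12.3 and 12.4.1 apply to SAEs, so they inherit the gap from Step 2.

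**Step 4. Does another data source recover it?**
- SAP Section 16.1.5 draws SAEs only from the adverse event source.
- The sample diary in Protocol Appendix III holds counts for four seizure codes, with no field for hospitalization and no code for status epilepticus.
- The diary is completed up to Visit 9 (Section 11.2.2.4). At the safety follow-up it is reviewed but not collected (Table 2, note q), and the SAP's seizure intervals end at Visit 9.
- Section 13 records a reason for stopping study drug, but only for subjects who stop, and this does not feed the SAE table.

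Neither document gives a route that would put an omitted admission into the SAE summary.

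**Step 5. Scale per omitted subject.** SAE incidence in an arm is subjects with at least one SAE divided by subjects in the safety population. Leaving out one subject whose only SAE was such an admission lowers it by 1/n. Taking n as the planned arm size, and assuming that every enrolled subject is dosed:

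| Source | Arm | n | 1/n |
|---|---|---|---|
| Protocol Section 15.1 | Arm 1 | 93 | 1.1 points |
| Protocol Section 15.1 | Arm 2 | 97 | 1.0 point |
| SAP Section 3.1 | Each arm | 50 | 2.0 points |

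The documents give no expected rate of seizure admissions and no basis for the share that sites would leave out, so a total cannot be calculated.

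**The case against.** The best answer is that 12.1.1 already does most of the work. Exclusion criterion 10 bars subjects with status epilepticus or cluster seizures in the 3 months before screening, so an on-study episode will usually be new against the recent pattern. That makes it a worsening in severity, pattern or type, which should be recorded. A seizure needing more than the subject's usual intervention also points towards greater severity. This stands, and it narrows the gap considerably. It does not close it: subjects with older episodes can enter, worsening is judged against the subject's own history, and an admission for a seizure of the usual kind need not count as a worsening.

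A second answer is a harmonised reading. Section 12.1.1 opens with a broad AE definition that includes exacerbation of pre-existing conditions, and exempts seizures only as a matter of routine. *May* could then mean that the exemption is lifted for non-routine events, after which the compulsory rules apply. That reading is possible, but the text does not require it. *May* stands directly before a sentence that uses *should*, and a site could fairly read the contrast as deliberate.

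Some stronger readings are tempting and lack support:
- A reader might infer that any admission for status epilepticus can be dropped at will. The worsening sentence and exclusion criterion 10 argue against that for most new episodes.
- A reader might infer that status epilepticus is an identified risk of the study drug. The documents contain no list of such risks; status is mentioned only in this sentence and as an exclusion.
- A reader might see this as a drug-withdrawal trial in which seizure admissions are to be expected. It is an add-on study with background drugs held constant apart from limited reductions (Section 10.2), and the taper applies only to subjects who stop the study drug.
- A reader might assume an admission rate and say that anything from none to all of those events could go unreported. The rate would have no source, and the range would ignore the events that should already be recorded.

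**Conclusion.** The concern holds in a narrow form. Sections 12.1.1 and 12.1.2 do not fit together for seizure events that lead to hospitalization: admission makes an AE serious, but does not make the seizure an AE that must be recorded. What remains optional is the admission that a site judges to be neither a worsening nor an adverse consequence. Such an event can be missing from the AE and SAE data, and nothing else in the plan recovers it.

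The size is about 1 percentage point of arm-level SAE incidence per omitted subject at the protocol's numbers, or 2 points at the SAP's, provided that the subject had no other SAE. The total is unknown. Any error in SAE incidence is towards too low a figure, but whether it arises depends on how sites use the discretion. The primary retention endpoint and the sample size are unaffected, and the plan has no between-arm comparison or test to distort. This is worth correcting because it concerns a stated safety endpoint and the trigger for sponsor review.

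**What to change.** Reconcile Section 12.1.1 with Section 12.1.2 by adding one sentence, for example: *Any seizure, cluster of seizures or episode of status epilepticus that meets a seriousness criterion in Section 12.1.2 must be recorded as an AE and reported as an SAE.* Keep the statement that ordinary seizures are not routinely AEs. Leave the wording for non-serious seizures as it is, because the gap shown here concerns only events that meet a seriousness criterion.

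The cost is a few more SAE reports, possibly a slightly higher SAE rate, and a minor protocol amendment, which under Section 17.5 needs written approval from the sponsor and the ethics board. The SAP derivation in Section 16.1.5 can stay as it is, since the added events would then reach the adverse event source.

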12.1.2. Serious Adverse Events

A SAE is an AE that meets one or more of the following criteria:

- Results in death.
- Is life-threatening.
- Requires hospitalization or prolongation of existing hospitalization.
- Results in persistent or significant disability or incapacity.
- Is a congenital anomaly or birth defect.
- Is an important medical event that may jeopardize the subject or may require a medical or surgical intervention to prevent one of the outcomes listed above.

Examples of such medical events include allergic bronchospasm requiring intensive treatment in an emergency room or at home, or blood dyscrasias.

The term “severe” is often used to describe the severity of a specific event (as in mild, moderate, or severe myocardial infarction) (see [Section 12.3](#)); the event itself, however, may be of relatively minor medical significance (such as severe headache). This is not the same as “serious,” which is based on subject/event outcome or action criteria usually associated with events that pose a threat to a subject’s life or functioning as defined by the criteria above.

During the study, if a subject has a hospitalization or procedure (eg, elective surgery) that was scheduled before the study entry, ie, before informed consent for an event/condition that occurred before the study, the hospitalization is considered a therapeutic intervention and not the result of a SAE. However, if the event/condition worsens during the study, it should be reported as an AE (or SAE, if the event/condition results in a serious outcome such as prolongation of hospitalization).

Life-threatening means that the subject was, in the view of the Investigator, at immediate risk of death from the event as it occurred. This definition does not include an event that had it occurred in a more severe form might have caused death.

SAE criteria information will be captured on the CRF.

